### 2.2. Background

Atopic dermatitis is a complex heterogeneous disease that is determined by genetic, environmental, and immunologic factors (Werfel et al. 2016; Simon et al. 2019). Genetic studies of AD (Bieber 2012; Auriemma et al. 2013; Weidinger et al. 2018) have shown that genes encoding for cytokines involved in the regulation of the immune system (IL-4, IL-5, and IL-13) are strongly associated with the development of AD (Novak et al. 2002; He et al. 2003;

Hummelshoj et al. 2003). In addition, variants of genes that encode for proteins involved in skin barrier function, such as filaggrin (FLG) and loricrin (LOR), are also associated with AD (Van Bever and Llanora 2011).

Reduced epithelial barrier function, which represents the first line of protection against the environment, is thought to lead to sensitization to environmental allergens, associated with elevated IgE (Werfel et al. 2016) and consistent with the presence in the skin of Type 2 cytokines (IL-4, IL-5, IL-9, IL-13, IL-25, IL-31, IL-33, and thymic stromal lymphopoietin) and inflammation. Type 2 cytokines increase epidermal thickening, sensitization, inflammation, and pruritus and decrease the expression of antimicrobial peptides and the barrier proteins FLG, LOR, and involucrin. Interleukin 13 in particular can reduce epithelial integrity and barrier function through downregulation of FLG, LOR, and involucrin (Kim et al. 2008) and can act on keratinocytes in the skin to downregulate their differentiation (Howell et al. 2008). Interleukin 13 also induces T-cell chemoattractants that mediate T-cell infiltration into AD lesions (Purwar et al. 2006) and may also induce IL-5 expression and eosinophil infiltration through the induction of eosinophil chemoattractants (Esche et al. 2004). Increased expression of IL-13 has consistently been reported in AD skin lesions and is associated with disease severity (Hamid et al. 1996; Jeong et al. 2003; Tazawa et al. 2004; La Grutta et al. 2005; Neis et al. 2006; Choy et al. 2012; Suárez-Fariñas et al. 2013).

A Phase 2b, double-blind, placebo-controlled study of adult participants with investigator global assessment (IGA) (3,4), Eczema Area and Severity Index (EASI) ( $\geq 16$ ), body surface area (BSA)  $\geq 10\%$ , chronic AD for at least 1 year, and for whom topical treatment was inadequate or inadvisable showed that participants taking lebrikizumab loading dose followed by 250 mg subcutaneous (SC) once every 2 weeks (Q2W) met primary endpoint criteria of EASI least-squares mean % change, with % change -72.1, p value  $< 0.001$ , at 16 weeks (Guttman-Yassky et al. 2020). Statistical significance was also reached for the secondary endpoints IGA 0,1 response, EASI50, EASI75, EASI90, mean percentage BSA involvement change from baseline, and Pruritus NRS change from baseline. The top-line results from 2 randomized, controlled, monotherapy Phase 3 studies of lebrikizumab (ADvocate 1 and ADvocate 2) and a third completed Phase 3 trial of lebrikizumab in combination with topical steroids (ADhere) demonstrated positive risk benefit in adult and adolescent patients with moderate-to-severe AD at Week 16.

Recruitment and inclusion of patients of color in dermatologic therapy trials, including AD studies, is historically limited (Chen et al. 2022). The Phase 2b lebrikizumab study included 16-28 (30.7% to 35.6%) Black or African American participants in each of the 4 arms of the study; 10% and 21% in pivotal Phase 3 studies respectively; these numbers are a significant increase compared to historical pharmaceutical dermatologic studies (Chen et al. 2022). However, more work is needed to fully characterize, support, and treat skin of color populations with AD. While these patient populations were represented in the clinical studies, further assessment in the context of a focused study and clinical assessments specific to patients of color will generate an expanded dataset on the benefit: risk balance of lebrikizumab in this patient group.

### **Epidemiology of Atopic Dermatitis**

There is a paucity of data describing the prevalence of AD in skin of color populations, with ranges of 6% to 15.89% in Black and/or African American race, 8% to 9.1% in Asian race, and 6% in Hispanic ethnicity in the United States (US) (Silverberg and Hanifin 2013). In

comparison, the 1-year prevalence of AD among adults in the US is estimated between 2% and 7% (Harrop et al. 2007; Chiesa Fuxench et al. 2018; Sacotte and Silverberg 2018), and approximately 30% of adult patients with AD have moderate-to-severe disease (Bieber and Straeter 2015).

### **Clinical Manifestations**

Clinically, AD is characterized by erythematous macules, papules, and/or plaques with scale, lichenification, and intense pruritus (Bieber 2008), which, along with the distribution, chronicity, and history of skin lesions, form the basis for making a diagnosis of AD. Flares are frequently triggered by exposure to environmental factors, irritants, and allergens (Bieber and Novak 2009). Several clinical patterns, with differing distributions of skin lesions in distinct age groups and skin types, have been noted (Weidinger and Novak 2016; Weidinger et al. 2018; Sangha 2021).

Classic AD lesions, which are most common in adolescents and adults, present on the antecubital and popliteal fossae. Lesions frequently localize to the face and neck, and a considerable portion of patients (around 30%) develop atopic hand dermatitis, which may interfere with workplace activities. Lesions may have associated lichenification and crusting, and patients with AD may be at increased risk for bacterial cutaneous superinfection.

Individuals of African descent may be more likely to present with lichenoid papules or profound xerosis (Jungersted et al. 2010, Muizzuddin et al. 2010), and erythema may be masked by pigmentation or appear purple, light brown or ashen gray. Perifollicular accentuation, a more scattered pattern, and greater extensor involvement are possible. In addition, there may be a greater burden of post-inflammatory hyperpigmentation and/or hypopigmentation in this population (Kaufman et al. 2018; Silverberg et al. 2019). Individuals of Asian descent may have AD features clinically consistent with both AD and psoriasis, with more well-demarcated, scaly plaques with greater lichenification and perifollicular accentuation (Noda et al. 2015; Kaufman et al. 2018; Brunner and Guttman-Yassky 2019). In contrast, patients of Hispanic ethnicity are at higher risk of severe, more recalcitrant AD, and may have greater trunk involvement (Wei et al. 2018; Silverberg et al. 2019).

### **Quality of Life**

Patients with AD have a high disease burden, and their quality of life is significantly affected. In one study, AD was shown to have a greater negative effect on patient mental health than diabetes and hypertension (Zuberbier et al. 2006). Patients with moderate-to-severe AD have a higher prevalence of social dysfunction and sleep impairment, which are directly related to the severity of the disease (Williams et al. 2008). Depression, anxiety, and social dysfunction not only affect patients with AD but also affect their caregivers (Zuberbier et al. 2006). Compared with patients with psoriasis, patients with AD have lower physical vitality, social functioning, emotional, and mental health scores (Kiebert et al. 2002). There are limited data specifically addressing quality of life (QoL) in patients with skin of color and AD. A study of almost 1000 adults with AD at a US academic center showed that more severe health-related QoL impairment was observed in Black and Asian patients (Schwartzman et al 2022). More robust data on the quality of life for patients with skin of color and moderate-to-severe AD are needed.

## Treatment for Atopic Dermatitis

The therapeutic approach to AD consists primarily of trigger avoidance, skin hydration, and use of moisturizers and anti-inflammatory therapies consisting predominantly of topical corticosteroids (TCS). For patients with deeper skin tones, it is also important to address the need for improvement or clearance of post-inflammatory hyperpigmentation and hypopigmentation (Davis and Callender 2010). In many patients, treatment with TCS provides some measure of symptomatic relief but does not always adequately control the disease. In patients with persistent moderate-to-severe disease not responding adequately to TCS, the step-up options include topical calcineurin inhibitors, phototherapy and immunosuppressive agents, such as oral or injected corticosteroids, cyclosporine, azathioprine, methotrexate, and mycophenolate mofetil. In 2017, dupilumab was approved for the treatment of adult patients with moderate-to-severe AD, and in 2021, an IL-13 antagonist, tralokinumab, was approved for adults with moderate-to-severe AD. Also in 2021, the topical Janus kinase (JAK) inhibitor ruxolitinib was approved for the treatment of mild-to-moderate AD in adults and children aged 12 and older, and in 2022, the oral JAK inhibitors, upadacitinib and abrocitinib, were approved for treatment of moderate-to-severe AD in adults and children aged 12 and older and adults, respectively. Despite these treatments, there remains a major societal burden for those with AD and a significant unmet medical need for treatment. Traditional systemic therapies, including cyclosporine, methotrexate, mycophenolate mofetil, and azathioprine, are not FDA approved, have potential side effects, and may require intensive lab monitoring; the JAKs, upadacitinib and abrocitinib, have a safety signal that may not be appealing for many patients and providers and are therefore commonly not chosen as first-line therapy, and although dupilumab and tralokinumab are approved biologics, specific studies on skin of color populations have not been completed, signaling a clinical care gap (Seegräber et al 2018; Gooderham et al 2018). This study will fill this clinical gap by evaluating the standard AD outcomes characterization of novel endpoints that are important for individuals with skin of color.

A detailed description of the chemistry, pharmacology, efficacy, and safety of lebrikizumab is provided in the Investigator's Brochure (IB).

### 2.3. Benefit/Risk Assessment

As of 22 September 2021, cumulatively, approximately 7795 participants have been enrolled into the lebrikizumab clinical program, of which approximately 6374 participants have received lebrikizumab. Lebrikizumab has been given to 525 healthy people and 5849 study participants with AD, asthma, chronic obstructive pulmonary disease, idiopathic pulmonary fibrosis, and Hodgkin's lymphoma. Approximately 2051 have been treated with lebrikizumab in the Phase 2 and Phase 3 AD programs.

The use of lebrikizumab for the treatment of AD is supported by numerous preclinical studies demonstrating that AD is characterized by the increased expression of IL-13 in skin. Moreover, Phase 2 efficacy studies of lebrikizumab (J2T-DM-KGAG/TREBLE, J2T-DM-KGAH/ARBAN, and J2T-DM-KGAF/DRM06-AD01) demonstrated significant clinical benefit in participants with AD. The top-line results from the 2 monotherapy Phase 3 studies of lebrikizumab (ADvocate 1 and ADvocate 2) achieved the primary and all key secondary endpoints, including skin clearance and itch improvement at Week 16. A third completed pivotal Phase 3 trial of lebrikizumab in combination with topical steroids (ADhere) also met all primary and key secondary endpoints at Week 16.

Potential risks associated with lebrikizumab include conjunctivitis, eosinophilia and eosinophilic conditions, herpes zoster and herpes infections (Section 8.3.3), anaphylaxis and hypersensitivity reactions (Section 8.3.5), and other infections (Section 8.3.3.1).

In the initial 16-week, placebo-controlled period of ADvocate 1 and ADvocate 2, the incidence of treatment-emergent adverse events (TEAEs) and serious adverse event (SAEs) among patients treated with lebrikizumab was consistent with that of the previous Phase 2 lebrikizumab studies in AD. The most common AEs included conjunctivitis, nasopharyngitis, and headache for lebrikizumab-treated patients. Discontinuations due to AEs were similar in the lebrikizumab group (1.4%) compared to placebo (1.7%). The safety profile of lebrikizumab observed in the 3 Phase 3 studies was found to be consistent with prior lebrikizumab studies in AD.

No immediate systemic hypersensitivity or anaphylaxis events were reported in the Phase 3 trials ADvocate 1, ADvocate 2, and ADhere. No parasitic or opportunistic infections were reported. No eosinophilic-related events were reported.

Participants will be monitored for these events and will be provided appropriate intervention or supportive care as needed. If events occur, additional testing and data collection may be required as described further in Section 8.3.3, 8.3.5, and 8.3.6.

Additionally, to monitor participant safety during the course of the study, the Sponsor will conduct trial-level safety reviews at periodic intervals throughout the study.

In summary, in the context of the cumulative knowledge for lebrikizumab, the benefit/risk balance is assessed to be acceptable for testing in this Phase 3b study.

More detailed information about the known and expected benefits and risks and reasonably expected adverse events of lebrikizumab may be found in the IB or Development Safety Update Report.

### 3. Objectives, Endpoints, and Estimands

Objectives	Endpoints
Primary	

 
To assess the effect of lebrikizumab 250 mg Q2W in reducing the signs and symptoms of AD in participants with moderate-to-severe AD and skin of color
 
	
 
Percentage of participants achieving EASI-75 (<math>\geq 75\%</math> reduction from baseline in EASI) at Week 16
 

Secondary	

 
To evaluate the effect of treatment with lebrikizumab in the signs and symptoms of AD and health outcome measures, in participants with moderate-to-severe AD and skin of color
 
	
 
Percentage of participants achieving EASI-75 at Week 24
 
Percentage of participants with an IGA score of 0 or 1 and a reduction <math>\geq 2</math> points from baseline to Weeks 16 and 24
 
Percentage change in EASI total from baseline to Weeks 16 and 24
 
Change in EASI total from baseline to Weeks 16 and 24
 
Percentage of participants achieving EASI 90 at Weeks 16 and 24
 
Percentage of participants with a Pruritus NRS of <math>\geq 4</math> points at baseline who achieve a 4-point reduction at Weeks 16 and 24
 
Percentage of participants with a Pruritus NRS <math>\geq 3</math> points at baseline who achieve at least 3-point reduction at Weeks 16 and 24
 
Percentage change in Pruritus NRS score from baseline to Weeks 16 and 24
 
Percentage of participants with a Sleep-Loss Scale score of <math>\geq 2</math> points at baseline who achieve a 2-point reduction at Weeks 16 and 24
 
Percentage change in Sleep-Loss Scale score from baseline to Weeks 16 and 24
 
Percentage of participants with a Skin Pain NRS of <math>\geq 4</math> points at baseline who achieve a 4-point reduction from baseline to Weeks 16 and 24
 
Change in POEM from baseline to Weeks 16 and 24
 
Change in DLQI from baseline to Weeks 16 and 24 for participants <math>\geq 16</math> years of age at baseline
 

	
 
• Change in cDLQI from baseline to Weeks 16 and 24 for participants <16 years of age at baseline
 
• Percentage of participants with a DLQI of <math>\geq 4</math> points at baseline who achieve a <math>\geq 4</math>-point improvement in DLQI at Weeks 16 and 24 for participants <math>\geq 16</math> years of age at baseline
 

Exploratory
	

 
• To evaluate the efficacy and health outcome measures of lebrikizumab from baseline by visit in participants with skin of color and moderate-to-severe AD
 
	
 
• Percentage change in PO-SCORAD from baseline by visit
 
• Change in Post-inflammatory Dyschromia Scale from baseline by visit
 
• Percentage change in ADCT from baseline by visit
 
• Using WPAI-AD by visit, change in baseline in             
 
○ absenteeism in those who are currently employed (working for pay)
 
○ presenteeism in those who are currently employed (working for pay)
 
○ overall work impairment in those who are currently employed (working for pay), and
 
○ impairment in activities (all participants)
 
 
 
• Percentage of participants with an F-IGA score of 0 or 1 and a reduction <math>\geq 2</math> points from baseline by visit
 
• Lichenification change from baseline (calculated from EASI)
 
• Participant satisfaction change from baseline (1 question)
 
• Percentage of participants achieving EASI-75 by visit
 
• Percentage of participants with an IGA score of 0 or 1 and a reduction <math>\geq 2</math> points from baseline by visit
 
• Percentage change in EASI total by visit
 
• Change in EASI total by visit
 
• Percentage of participants achieving EASI-90 by visit
 

	
 
• Percentage of participants with a Pruritus NRS of <math>\geq 4</math> points at baseline who achieve a 4-point reduction by visit
 
• Percentage of participants with a Pruritus NRS of <math>\geq 3</math> points at baseline who achieve a 3-point reduction by visit
 
• Percentage change in Pruritus NRS score by visit
 
• Percentage of participants with a Sleep-Loss Scale score of <math>\geq 2</math> points at baseline who achieve a 2-point reduction by visit
 
• Percentage change in Sleep-Loss Scale score from baseline by visit
 
• Percentage of participants with a Skin Pain NRS of <math>\geq 4</math> points at baseline who achieve a 4-point reduction from baseline by visit
 
• Change from baseline in POEM by visit
 

 
• To discern responder variability within the study and to track response variability to lebrikizumab
 
	
 
• Changes from baseline in serum proteins related to AD pathogenesis: Refer to Appendix 2
 

Abbreviations: AD = atopic dermatitis; ADCT = atopic dermatitis control tool; cDLQI = Children’s DLQI; DLQI = Dermatology Life Quality Index; EASI = Eczema Area and Severity Index; F-IGA = face-IGA; IGA = Investigator’s Global Assessment; NRS = numeric rating scale; PDS = Post-inflammatory Dyschromia Scale; POEM = Patient-Oriented Eczema Measure; PO-SCORAD = Patient-Oriented SCORing Atopic Dermatitis; Q2W = once every 2 weeks; WPAI-AD = Work Productivity and Activity Impairment Questionnaire–Atopic Dermatitis.

NOTE: Endpoints in the table above collected by visit references data collection visits.

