### **8.1.5. Post-inflammatory Dyschromia Scale (PDS)**

The PDS is an investigator assessment of cutaneous post-inflammatory hyperpigmentation and/or hypopigmentation which is completed at the visit per the SoA. This is a measure of post-inflammatory cutaneous change; as such, pigmented actively inflamed AD lesions should not be evaluated with this scale. Areas of normal pigmentation, with no post-inflammatory hyper- or hypo- pigmentation, will receive a score of 0. Areas of post-inflammatory hyperpigmentation, as compared to adjacent normal skin tone (0), should receive a score of 1 (mild/barely perceptible hyperpigmentation), 2 (moderate/clearly perceptible hyperpigmentation) or 3 (severe/prominent hyperpigmentation). Areas of post-inflammatory hypopigmentation, as compared to adjacent normal skin tone (0), should receive a score of -1 (mild/barely perceptible hypopigmentation), -2 (moderate/clearly perceptible hypopigmentation) or -3 (severe/prominent hypopigmentation).

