Secondary Endpoints: 
 Percentage of participants achieving EASI-75 at Week 24 Percentage of participants with an IGA score of 0 or 1 and a reduction ≥ 2 points from baseline to Weeks 16 and 24 Percentage change in EASI total from baseline to Weeks 16 and 24 Change in EASI total from baseline to Weeks 16 and 24 Percentage of participants achieving EASI 90 at Weeks 16 and 24 Percentage of participants with a Pruritus NRS of ≥ 4 points at baseline who achieve a 4-point reduction at Weeks 16 and 24 Percentage of participants with a Pruritus NRS ≥ 3 points at baseline who achieve at least 3-point reduction at Weeks 16 and 24 Percentage change in Pruritus NRS score from baseline to Weeks 16 and 24 Percentage of participants with a Sleep-Loss Scale score of ≥ 2 points at baseline who achieve a 2-point reduction at Weeks 16 and 24 Percentage change in Sleep-Loss Scale score from baseline to Weeks 16 and 24 Percentage of participants with a Skin Pain NRS of ≥ 4 points at baseline who achieve a 4-point reduction from baseline to Weeks 16 and 24 Change in POEM from baseline to Weeks 16 and 24 Change in DLQI from baseline to Weeks 16 and 24 in participants ≥ 16 years of age at baseline Change in cDLQI from baseline to Weeks 16 and 24 in participants < 16 years of age at baseline Percentage of participants with a DLQI of ≥ 4 points at baseline who achieve a ≥ 4-point improvement in DLQI at Weeks 16 and 24 in participants ≥ 16 years at baseline
Exploratory Endpoints: 
 Change from baseline in body surface area (BSA) by visit Percentage change in PO-SCORAD from baseline by visit Change in Post-inflammatory Dyschromia Scale (PDS) from baseline by visit Percentage change in ADCT from baseline by visit Using WPAI-AD by visit, change in baseline in 
 o absenteeism in those who are currently employed (working for pay) o presenteeism in those who are currently employed (working for pay) o overall work impairment in those who are currently employed (working for pay), and o impairment in activities (all participants) Percentage of participants with an F-IGA score of 0 or 1 and a reduction ≥ 2 points from baseline by visit Lichenification change from baseline (calculated from EASI) Participant satisfaction change from baseline (1 question)

- Percentage of participants achieving EASI-75 by visit

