5.1.2 General Considerations for Analyses

All analyses will be descriptive. Frequencies, percentages, and 90% Wilson-Score CIs for percentages will be reported for discrete efficacy endpoints. Mean, standard deviation, minimum, Q1, median, Q3, maximum, and the number of participants will be reported for continuous

efficacy endpoints. AEs, discontinuation, and other categorical safety data will be summarized using frequencies and percentages. Continuous vital signs, body weight, and other continuous safety variables including laboratory variables will be summarized descriptively as well.

Baseline

Baseline will be defined as the last available value before the first injection for efficacy and health outcome analyses. In most cases, this will be the measure recorded at the baseline visit (Day 1). If the patient does not take any injection, the last available value on or prior to treatment assignment date will be used. Change from baseline will be calculated as the visit value of interest minus the baseline value.

For Pruritus Numeric Rating Scale (NRS), Skin Pain NRS, and Sleep-Loss due to Pruritus collected via eDiary, the baseline period is the 7-day window prior to the first injection. A patient must have responses on at least 4 of 7 days to calculate a baseline weekly mean. If a patient has 3 or fewer responses, the baseline mean value will be considered missing.

For the safety analyses, the following baselines will be used. For safety analyses using a baseline period, the baseline period is defined as the time from the screening visit to the date/time of the first injection.

- TEAEs: baseline will be all results recorded during the baseline period.
- Treatment-emergent abnormal laboratory and vital signs results: baseline will be all results recorded during the baseline period.
- Change from baseline to last post-baseline observation or to each scheduled postbaseline visit for laboratory and vital signs results: baseline will be the last scheduled non-missing assessment recorded during the baseline period.

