5.8.3 Prespecified Clinical Events

The number and percentage of patients with prespecified clinical events (including Follicular/Perifollicular accentuation of atopic dermatitis, Allergic shiner(s), Pityriasis alba, Prurigo, Eczema nummular, Eczema facial, and Hand eczema) on the *Prespecified Clinical Events* eCRF at baseline and Week 24 will be summarized. For those who reported a prespecified clinical event at baseline and who remained on treatment until Week 24, the number and percentage of patients shifting from a higher severity at baseline to a lower severity or no event at Week 24 (e.g., severe at baseline to moderate, mild, or no event at Week 24) will be reported. The number and percentage of patients shifting from a lower severity or no event at baseline to a higher severity at Week 24 (e.g., no event at baseline to mild, moderate, or severe at Week 24) will also be reported.

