5.11 Efficacy Analyses

Table KGBP.5.4 includes the description and derivation of the efficacy measures and endpoints.

For categorical parameters, the number and percentage of patients in each category will be presented, as well as a 90% Wilson-Score confidence interval for the percentage. For continuous parameters, descriptive statistics will include n (number of patients), mean, standard deviation, Q1, median, Q3, minimum, and maximum. These summaries will be provided for the data as-observed and after implementation of LOCF and MCMC-MI imputation as described in Sections 5.4.2 and 5.4.3.

The IGA, F-IGA, EASI, BSA, Pruritus NRS, Skin Pain NRS, and Sleep-Loss Scale will be reported by clinic visit.

Table KGBP.5.4. Description and Derivation of Efficacy/Health Outcomes Measures and Endpoints

Measure	Description	Variable	Derivation/Comment	Imputation Approach if Missing Components
Investigator's Global Assessment (IGA)	The IGA is a static assessment and rates the severity of a patient's AD. The IGA is comprised of a 5-point scale ranging from 0 (clear) to 4 (severe), and a score is selected using descriptors that best describe the overall appearance of the lesions at a given time point.	IGA score	Single item. Range: 0-4 0 represents "clear" 4 represents "severe"	Single item, missing if missing
		• IGA (0,1) with ≥ 2 -point improvement ^a IGA (0)	• Observed score of 0 or 1 and change from baseline ≤ 2 Observed score of 0	Missing if baseline or observed value is missing Single item, missing if missing
Face-Investigator's Global Assessment (F-IGA)	The F-IGA is a static assessment and rates the severity of a patient's AD on the face. The F-IGA is comprised of a 5-point scale ranging from 0 (clear) to 4 (severe), and a score is selected using descriptors that best describe the overall appearance of the lesions at a given time point.	F-IGA Score	Single item. Range: 0-4, 0 represents "clear", 4 represents "severe"	Single item, missing if missing
		F-IGA (0,1)	Observed score of 0 or 1	Missing if baseline or observed value is missing
		F-IGA (0)	Observed score of 0	Single item, missing if missing

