Post-Inflammatory Dyschromia Scale (PDS)	The PDS is an investigator assessment of cutaneous post-inflammatory hyperpigmentation and/or hypopigmentation which is completed at the visit per the SoA	Post-inflammatory cutaneous change in pigmentation.	0: Areas of normal skin tone 1: Areas of post-inflammatory hyperpigmentation, (mild/barely perceptible hyperpigmentation), 2: Areas of post-inflammatory hyperpigmentation, (moderate/clearly	Single item, missing if missing.	

			perceptible hyperpigmentation) 3: Areas of post-inflammatory hyperpigmentation, (severe/prominent hyperpigmentation). -1: Areas of post-inflammatory hypopigmentation, (mild/barely perceptible hypopigmentation), -2: Areas of post-inflammatory hypopigmentation, (moderate/clearly perceptible hypopigmentation) -3 Areas of post-inflammatory hypopigmentation, (severe/prominent hypopigmentation)	

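### The PDS change score is signed around a normal value of 0, so its sign, or a pooled mean or median of it, cannot tell improvement from worsening

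*Protocol*

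**What the plan says.** Protocol Section 3 lists "Change in Post-inflammatory Dyschromia Scale from baseline by visit" as an exploratory endpoint. SAP Section 3 (Table KGBP.3.1) repeats it as "Change in Post-inflammatory Dyschromia Scale (PDS) from baseline by visit".

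Protocol Section 8.1.5 scores normal pigmentation 0 and hyperpigmentation 1 to 3. Areas of hypopigmentation "should receive a score of -1 (mild/barely perceptible hypopigmentation), -2 (moderate/clearly perceptible hypopigmentation) or -3 (severe/prominent hypopigmentation").

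SAP Section 5.1.2 sets the general rule: "Change from baseline will be calculated as the visit value of interest minus the baseline value". For summaries, SAP Section 5.11 states: "For continuous parameters, descriptive statistics will include n (number of patients), mean, standard deviation, Q1, median, Q3, minimum, and maximum". Categorical parameters get counts, percentages and a 90% Wilson interval per category.

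The PDS row of SAP Table KGBP.5.4 lists the seven codes and gives a missing-data rule, "Single item, missing if missing". It names no change variable and does not say whether PDS is continuous or categorical. For the prespecified clinical events, by contrast, SAP Section 5.8.3 plans to report "the number and percentage of patients shifting from a higher severity at baseline to a lower severity or no event at Week 24", and the reverse shift as well.

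**The concern.** The visit-minus-baseline rule works for a scale on which higher is always worse. On PDS the best value lies in the middle. A negative change is benefit for someone with hyperpigmentation and harm for someone with hypopigmentation, and a positive change is the reverse. Once the two groups are pooled, the mean or median change no longer has a clinical direction.

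Both types are foreseen. In the Clinical Manifestations part of Protocol Section 2.2, on individuals of African descent, the protocol says "there may be a greater burden of post-inflammatory hyperpigmentation and/or hypopigmentation in this population". The Rationale in Protocol Section 1.1 names PDS among the study's novel endpoints. A pooled signed result could hide real benefit, overstate it, or point the wrong way.

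There is a smaller, related gap. The scale's definitions score areas of skin, while the SAP handles PDS as one item. No rule covers a participant who has both hyperpigmented and hypopigmented areas.

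**Working it through.** The plan states no figure for PDS, so there is none to reproduce. The check has two parts.

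**1. Does the sign of the change carry direction?** Let b be the baseline score and v the visit score, each from -3 to +3. The plan's change is v - b. The change in distance from normal is |v| - |b|, where negative means improvement. Over all 7 x 7 = 49 pairs:

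| Signed change | Pairs | Improve | Worsen | Same severity |
|---|---|---|---|---|
| Positive | 21 | 9 | 9 | 3 |
| Negative | 21 | 9 | 9 | 3 |
| Zero | 7 | 0 | 0 | 7 |

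This is structural. The move from b to v and the mirrored move from -v to -b have the same signed change and opposite effects on distance from normal. For example, +2 to 0 and 0 to -2 both score -2.

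Whole samples can be indistinguishable too. Take 80 participants:
- 48 with hyperpigmentation and 32 with hypopigmentation, all improving by 1 grade: 48 values of -1 and 32 of +1.
- 32 with hyperpigmentation and 48 with hypopigmentation, all worsening by 1 grade: 32 values of +1 and 48 of -1.

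The two sets of change values are identical (mean -0.2, median -1). No statistic computed from the changes alone can separate them.

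**2. How large can the distortion be?** Let h be the share with hyperpigmentation. It is assumed here, because the documents give no mix; n = 80.

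*Scenario A: everyone resolves from 2 grades to 0.* Signed mean = -2h + 2(1 - h). The mean change in |PDS| is -2.0 whatever h is.

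| h | Signed mean | Change in absolute PDS |
|---|---|---|
| 0.5 | 0.0 | -2.0 |
| 0.6 | -0.4 | -2.0 |
| 0.7 | -0.8 | -2.0 |
| 0.8 | -1.2 | -2.0 |
| 1.0 | -2.0 | -2.0 |

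At h = 0.5 the SD is 2.01, Q1 is -2, the median is 0 and Q3 is +2. The spread shows heterogeneity but does not say that all of it is benefit.

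*Scenario B: hyperpigmentation improves (+2 to 0), hypopigmentation worsens (-1 to -2).* Signed mean = -2h - (1 - h); change in |PDS| = -2h + (1 - h).
- h = 0.5: signed -1.5, against -0.5.
- h = 0.8: signed -1.8, against -1.4.

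Read with negative as benefit, the signed mean overstates benefit.

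*Scenario C: hyperpigmentation worsens (+1 to +2), hypopigmentation improves (-2 to 0), h = 0.5.* Signed mean = 0.5 + 2(0.5) = +1.5; change in |PDS| = 0.5 - 2(0.5) = -0.5. The sign is reversed.

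**Does the proposed measure recover direction?** With the sample split by baseline sign and no crossing of 0, all 6 possible negative changes from a positive baseline are improvements and all 3 positive ones are worsenings. From a negative baseline it is the exact mirror. One case escapes |PDS|: a move from +2 to -2 has signed change -4 but change in |PDS| of 0, so a shift table is needed as well.

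**The case against.** The strongest reply is that the change column need not be the only PDS output. SAP Section 5.8.1 lists PDS among the instruments summarised at baseline, and Section 5.4.1 promises observed-data summaries of all efficacy data at each postbaseline visit. If the scores are tabulated by category, Scenario A would be plain: half at +2 and half at -2 at baseline, everyone at 0 later. The SAP never says PDS will be treated as continuous, so a pooled mean is an inference. This stands as far as it goes. But those tables show the distribution at each visit, not who moved. With 40 participants at +1 and 40 at 0 on both occasions, either nobody changed, or all 40 resolved while the other 40 developed new hyperpigmentation. The endpoint is change, and per-visit percentages do not answer it.

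The sizes above also depend on an assumed mix, and with one type only there is no cancellation. That is true. The ambiguity of the sign does not depend on the mix; its size does.

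The absolute score treats a grade of hyperpigmentation as equal to a grade of hypopigmentation. The scale uses the same mild, moderate and severe labels on both sides, which supports this but does not prove it. Reporting by baseline sign largely removes the reliance on it.

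Finally, the endpoint is exploratory, and both Protocol Section 9.3.1 and SAP Section 5.1 leave room for additional analyses. The tables could be added later, but choosing what counts as improvement after seeing open-label data is weaker than writing it down first. The subgroup plan (SAP Section 5.14) does not help: it covers EASI-75 only and has no split by baseline PDS.

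On mixed areas, the single-item wording sits in a missing-data column and is not a proven contradiction. It remains an open question that the CRF would settle.

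**Conclusion.** The concern holds. The plan's own change rule, applied to a scale with normal in the middle, gives a result that cannot separate improvement from worsening unless baseline direction is known, and no planned PDS output supplies that link. In the worked cases the pooled mean runs from complete cancellation (0.0 against a true 2-grade improvement at 50/50) to no distortion (one type only). It can overstate benefit (-1.5 against -0.5) or reverse its sign (+1.5 against -0.5) when the two types move differently. These sizes rest on assumed mixes and movements. That PDS will be summarised as a pooled mean is the natural reading of a change endpoint, but it is not stated.

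The primary and secondary results are untouched and no decision depends on PDS. The change is still worth making, because this endpoint is part of what the study offers beyond standard atopic dermatitis measures.

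**What to change.** Amend the PDS row of SAP Table KGBP.5.4:

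1. Define the change variable as |PDS| at the visit minus |PDS| at baseline, with negative meaning improvement, and state whether it is summarised as continuous or categorical.
2. Report it by baseline sign: above 0, 0 and below 0.
3. Add a baseline-by-visit shift table over the codes -3 to +3 for Weeks 16 and 24, the scheduled on-treatment PDS visits after baseline. It captures crossings of 0 and new dyschromia in participants who start at 0.
4. Do not use the pooled signed change as the summary.
5. State whether one score or several area scores are recorded per participant. If areas of opposite sign can be recorded, derive the hyperpigmentation and hypopigmentation scores separately and do not net them.

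The cost is SAP wording, one exploratory table and one shift table, all from scores already to be collected. This assumes the CRF, which is not in the documents, keeps the signed score or the separate area scores. If it stores only a netted value, opposite changes within a participant cannot be recovered.
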